In aim 1, we will assess the feasibility of a tele-delivered behavioral change intervention among older adults (aged 50 and older) with cLBP and depression. Fifty participants will be randomly assigned to one of two groups, behavioral intervention arm (n=25) versus the waitlist control arm (n=25). The active intervention will include eight tele-delivered health coach sessions and three tele-based outcome assessments. Each tele-based outcome assessment is roughly 45-60 minutes, and will be conducted by a member of the research team and will be recorded for research purposes. Each intervention session will be delivered by a trained health coach over a period of 10-20 weeks (up to 5 months total, accounting for additional time between sessions if needed). Aim 2 will involve one, in-depth, telephone-based, semi-structured interview at 6 months post-intervention. The health coach/research coordinator will identify participants who are at higher risk for drop-out, less engaged, or particularly successful at achieving behavioral change. The purpose of this interview is to learn about the barriers and facilitators to successful intervention delivery and integration within primary care, participant retention and acceptability from the clinician, patient, and health coach perspective. We will explore factors that are critical to eventual uptake of MOTIVATE; informed by Proctor's Framework of Implementation Outcomes we will focus on acceptability, adoption, appropriateness and sustainability of MOTIVATE. Semi-structured interviews with patients will be occur over the telephone, while clinician semistructured interviews can occur over the telephone or at a location convenient for the participant-most likely to occur on a UTSW or Parkland location.

The first session will introduce the participant to the health coach and the program, establish rapport, and measure baseline physical activity. The following six sessions address behavioral determinants, followed by a final session designed to be a booster session to the overall program.

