Since we are interested in better understanding feasibility of the intervention as compared to the waitlist control, and how behaviors are sustained over time, the study involves extended follow-up to six months. We will use these extended follow-up data to better understand differential attrition as well as preliminary formative implementation evaluation. Using purposive sampling, we will conduct ~ 16 indepth semi-structured interviews, 10 participants, 5 clinicians, and the health coach. Each interview will occur post-intervention and will include key stakeholders from the following groups: study participants from each arm of the pilot study, the health coach, primary care providers (including clinic leadership, geriatricians, and clinical psychologists- will be identified by the PI's professional network and via snow ball sampling), and will be audio recorded (on LRX 40 USB or UTSW digital logger) for research purposes. Each audio recording will, thereafter, be transferred to a secure folder, behind the UTSW firewall and deleted from the audio recording device. . The research staff will select participants identified as higher risk for drop-out, less engaged, or were particularly successful at achieving behavioral change. The purpose of the final interviews is to learn about the barriers and facilitators to successful intervention delivery and participant retention from the perspectives of the enrolled patients, health coach, and providers. Interview topics will borrow from components of the well-established framework, Promoting Action on Research Implementation in Health Services (PARiHS). Semi-structured interview strategy is informed by two PARiHS dimensions: context-how the microsystem (UTSW and or Parkland) impacts behavioral change uptake, for example, potential facilitators to intervention implementation; facilitation-identifying specific ways to augment the likelihood of implementation. Table 1 outlines the structure of the interview questions.

Table 1. Key Informant Interview Topics Based on PARiHS Framework of Evidence, Context, and Facilitation							
PARiHS Dimension: Evidence	PARiHS Dimension: Context	PARiHS Dimension: Facilitation					

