Proposed Analyses

Exact binomial method will be used to estimate rates of recruitment, intervention adherence, retention, and drop-out along with the corresponding 95% confidence intervals. Multiple levels of treatment retention will be defined, including partial intervention completion (% who do not complete all sessions), intervention dropout (% who dropout of intervention but continue to do assessments), research dropouts (% who remain in intervention, but do not complete assessments), and intervention + research dropouts (% who do not complete intervention or assessments). We will further break down the enrollment and retention calculations by examining enrollment/retention differences by treatment group, health coach, sex, age, race/ethnicity, and initial cLBP and depression severity using cross-classification tables.

As exploratory analyses, pre- and post-improvement in disability (RMDQ) and depression (PHQ-9) scores, as well as secondary and intermediate outcomes, from baseline to three months will be compared based on a two-sample t-test or Wilcoxon rank-sum tests between the two groups. The difference in improvement will be estimated and the 95% confidence interval will be reported. We will

estimate the preliminary effect size and variance of effect for the above outcomes. Linear mixed models will be used to assess whether there is a difference in the above outcomes over time within and between the two groups. We will include distance (in miles) from a UTSW or Parkland facility as a covariate in the exploratory outcome analyses, as suggested by reviewer.

We will describe, for the subset of participants receiving the intervention, whether physical activity (proximal outcome) and clinical outcomes (disability and depression scores) change over time based on the 1) proportion of the total sessions completed, and 2) the proportion of individual sessions completed. This will help us estimate optimal dose of the intervention (for example, whether completion of 4 vs. 7 vs. 8 of 10 sessions produces similar outcomes) and may inform which specific sessions are absolutely critical. SAS (version 9.3, Cary, NC) statistical software will be used.

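### The reported RMDQ and PHQ-9 arm difference rests on a change score that leaves out anyone without a final score; take it from the mixed model already planned

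*Combined protocol and SAP*

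**What the plan says.** All of the relevant analysis text is in the Proposed Analyses section of the combined protocol and SAP.

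- **Outcomes and status:** "As exploratory analyses, pre- and post-improvement in disability (RMDQ) and depression (PHQ-9) scores, as well as secondary and intermediate outcomes" are to be compared, so the analysis is openly exploratory.
- **Test:** the comparison runs "from baseline to three months will be compared based on a two-sample t-test or Wilcoxon rank-sum tests between the two groups".
- **Estimate:** the next sentence reads "The difference in improvement will be estimated and the 95% confidence interval will be reported".
- **Use:** the plan will then "estimate the preliminary effect size and variance of effect for the above outcomes".
- **Second analysis:** "Linear mixed models will be used to assess whether there is a difference in the above outcomes over time", within and between the arms. No estimation method, covariance structure or missing-data assumption is given for it.

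The same section defines several levels of retention. Two involve missed assessments: research dropouts, and "intervention + research dropouts (% who do not complete intervention or assessments"). A third class, intervention dropouts, stops coaching but continues assessments. The Study Design section adds, of the six-month data, "We will use these extended follow-up data to better understand differential attrition".

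Table 2 schedules both RMDQ and PHQ-9 at baseline, MID and END. The Outcome Assessments and Data Collection section puts MID at about 5 weeks and END at about 10 weeks. No analysis set, missing-data method or sensitivity analysis appears anywhere.

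**The concern.** A two-sample test on improvement can use only participants with both a baseline and a final score. The plan reads as attaching its one explicit estimate and interval to that test. The mixed model could also use participants who gave a MID score and were then lost, but it is asked only whether a difference exists. Two analyses of the same outcomes would therefore rest on different participants, and the reported number would come from the one that discards data already collected.

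What is at stake is planning, not a confirmatory claim. The Feasibility Outcomes and Analysis sections say the pilot is to inform a larger trial. An effect size and variance distorted by selective loss would be a poor input to that trial's design, whether too large or too small.

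**Working it through.** **Inputs from the documents.** 25 randomised per arm; RMDQ and PHQ-9 at baseline, MID and END. No SD, effect size, power or drop-out rate is stated, so there is no figure of the plan's own to reproduce.

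**Step 1: who is in each analysis.**

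| Participant | Change-score test | Mixed model on all scores |
|---|---|---|
| Stops coaching, END score given | in | in |
| END missing, MID given | out | in, through baseline and MID |
| END and MID missing | out | in, through baseline only |

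**Step 2: the bias in closed form.** In one arm, let p be the fraction without an END score, C the mean change in those with one, and M the (unseen) mean change in the rest. The mean for all randomised is (1−p)C + pM, so C exceeds it by p(C−M). Write g = C−M. The bias in the arm difference is then

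p_I·g_I − p_C·g_C (I = intervention, C = control).

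Lower PHQ-9 is better, so a negative value favours MOTIVATE. The bias vanishes if loss is unrelated to change, or if loss and mechanism are the same in both arms.

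**Step 3: numbers with no true effect.** All of these are assumptions: PHQ-9 SD 5; correlations 0.6 (baseline–MID), 0.5 (baseline–END) and 0.7 (MID–END); logistic drop-out with slope 1 per SD; 400,000 simulated per arm. When drop-out follows poor change by MID, g is about −3 points.

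| Loss I / C | Driver | Closed form | Simulated completer bias | Likelihood estimate |
|---|---|---|---|---|
| 23% / 10% | MID change, both arms | 0.23×(−3) − 0.10×(−3) = −0.39 | −0.4 | about 0 |
| 23% / 10% | MID change in I, random in C | 0.23×(−3) − 0 = −0.69 | −0.7 | about 0 |
| equal | MID change, both arms | 0 | about 0 | about 0 |
| 10% / 30% | MID change, both arms | 0.10×(−3) − 0.30×(−3) = +0.60 | +0.55 | about 0 |
| 23% / 10% | unseen END change | – | −0.5 to −1.0 | −0.3 to −0.5 |
| 23% / 10% | MID level only | – | −0.1 or smaller | about 0 |

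The first two rows are 0.4/5 = 0.08 SD and 0.7/5 = 0.14 SD.

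**Step 4: a second set with a true effect of 0.50 SD** (correlations 0.6/0.5/0.6, the worst responders leave; also assumed).

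| Loss I / C | MID-driven: completers | MID-driven: likelihood | END-driven: completers | END-driven: likelihood |
|---|---|---|---|---|
| 20% / 20% | 0.50 | 0.50 | 0.50 | 0.50 |
| 20% / 10% | 0.58 | 0.50 | 0.64 | 0.60 |
| 30% / 10% | 0.65 | 0.50 | 0.77 | 0.70 |
| 40% / 10% | 0.72 | 0.50 | 0.90 | 0.81 |
| 10% / 30% | 0.35 | 0.50 | 0.23 | 0.29 |

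If only the baseline score is available for those lost, the MID-driven likelihood estimates for 20/10, 30/10 and 40/10 are 0.55, 0.60 and 0.65. The gain therefore depends on MID having been observed.

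**Step 5: bias against precision.** With SD 5 and baseline–END correlation 0.5, the SD of change is 5×√(2×(1−0.5)) = 5. Loss of 23% and 10% from 25 leaves about 19 and 22. The 95% half-width is 2.02×√(1/19+1/22)×5 ≈ 3.2 points. A bias of 0.4 to 0.7 is 0.4/3.2 ≈ 13% to 0.7/3.2 ≈ 22% of that.

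**The case against.** The strongest reply is that the remedy is already in the plan. The mixed model covers the same outcomes in the same paragraph, and the only gap is which of two exploratory analyses supplies the reported number. Step 5 adds that, under the assumed loss, the bias is small beside an interval of about ±3.2 points. Both points stand. They make this a matter of wording in a feasibility pilot, but they do not settle where the estimate comes from.

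Stronger readings are tempting, and the documents do not support them:

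- **That the effect will be overstated.** This needs loss that is heavier, or more closely tied to outcome, in the intervention arm. Eight coaching sessions for one arm only, and a deferred offer of treatment for the other, make that conceivable, but no passage states it. The 10%/30% rows show the opposite.
- **That the plan forecasts unequal attrition.** The retention classes are defined in order to be measured. The Study Design section treats differential attrition as something to understand from the extended follow-up.
- **That all dropouts are removed.** Intervention dropouts who continue assessments keep their END score.
- **That participants who stop sessions leave their arm.** The two groups are the randomised arms, and no per-protocol set is defined. The analysis by sessions completed is a separate description within the intervention arm.
- **That the effect size certainly comes from completers.** Its sentence stands between the t-test and the mixed model and is assigned to neither.

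**Conclusion.** The point holds in a limited, direction-neutral form. The reported difference and interval are tied to a test that excludes participants without a final score, although scores already collected would let a planned model keep them. The estimate is biased only if loss is related to outcome and differs between arms in amount or mechanism.

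No size can be derived from the documents. The figure of 0.4 to 0.7 PHQ-9 points rests entirely on the assumed SD, correlations, 23%/10% loss and MID-driven mechanism. The mixed model removes that bias when drop-out depends on observed scores, and only part of it when drop-out depends on the unseen END score. Because the analysis is exploratory, the consequence is a possibly misleading planning estimate. The change is worth making before the data are analysed, but it does not threaten the feasibility aim.

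**What to change.** In Proposed Analyses:

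1. State that the END arm difference, 95% confidence interval, effect size and variance for RMDQ and PHQ-9 come from the linear mixed model. Fit it by likelihood to all randomised participants with at least one score, in the assigned arm whatever the number of sessions attended, with visit as a category and arm-by-visit terms.
2. Keep the t-test or Wilcoxon test on change as a supportive completer analysis, reporting the number of participants in each arm.
3. State that the model assumes data are missing at random. Add a simple sensitivity analysis in which missing END scores are worse than the model predicts, in one arm and then in both.
4. Reconcile three months in this section with the end-point at about 10 weeks in Outcome Assessments and Data Collection, so that the visit being estimated is unambiguous.

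The cost is wording and a short additional analysis; no new data are needed, and the model is already planned. The small downside is reliance on a model with about 25 participants per arm, so its covariance structure should be named in advance.

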Older adults urgently need effective behavioral interventions that simultaneously target cLBP and depression. Multiple studies demonstrate the effectiveness of non-pharmacological therapies in improving chronic pain outcomes, including therapies based on cognitive behavioral principles and/or movement-based strategies (exercise and physical therapy). We know that physical activity is effective (alone or as augmentation therapy) for adults with depression. A recent publication provides evidence that biopsychosocial multi-component interventions are more effective for patients (average age 45) with cLBP as compared to placebo or physical treatments. However, older adults are consistently excluded from studies for various reasons, mostly having to do with multi-morbidity and polypharmacy. There are no multicomponent tele-based behavioral interventions specifically in older adults with cLBP and depression. Because cLBP and depression are mutually perpetuating and exacerbating, a critical piece of this research is to identify and target interrelated behavioral determinants (i.e., beliefs, fear avoidance, self-efficacy, and motivation) that play a role in older adult's behavior and subsequent outcomes.

Overview of Proposed Intervention

The suggested intervention is grounded in health behavior theories and builds on prior interventions for chronic pain and mental illness in medically complex older adults. Our conceptual model includes patient characteristics, potential reciprocal relationships between the listed constructs, and emphasizes motivation to change as a key behavioral determinant (Figure 1). One-way arrows show that baseline socio-cultural variables, rarely modifiable, influence biopsychosocial factors (i.e. the way an older adult may experience pain) which in turn influence behavioral determinants. The extent and status of specific behavioral determinants may influence/modify specific baseline biopsychosocial factors, as well as both proximal and distal outcomes.

Figure 1: Conceptual Model for Proposed Intervention

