Our formative evaluation may help to identify parts of the process that need refinement to maximize the feasibility and extension of the project to different sites in the future. Also part of the formative evaluation process will be to understand how implementation factors influence the optimal dose of our intervention. This evaluation may highlight which intervention components (or active ingredients) resulted in a change in behavior or other outcome result and potentially why (barriers/facilitators of change from an implementation standpoint).

Potential Risks

The risks to the study are minimal. The research involves a tele-delivered program by a health coach over 10-20 weeks followed by an interview; hence, there is minimal risk of physical injury. Participants will be asked to be more physically active and track their steps with a pedometer. As they become more active there is a risk of fall and injury. However, the health coach will focus on safely increasing walking and fall prevention strategies. The amount of activity we are asking participants to do is considered standard of practice and not strenuous activity that could result in injury. Another possible risk to patients is loss of time and potential breach of confidentiality. Risks include participant burden and resulting fatigue. There is no economic or legal risk in this study. To prevent or minimize any potential risks, patients may stop the interview at any point during this study if they feel any distress.

Discussing pain or psycho-social factors including comorbid depression may result in further psychological distress. There is no economic or legal risk in this study. To prevent or minimize any potential risks, the participant may stop the health coaching, assessments, or interview process at any time.

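### The dose example counts 10 sessions in an eight-session programme, and non-randomised attendance in about 25 people can raise hypotheses about dose but cannot estimate an optimal one

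*Combined protocol and SAP*

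**What the plan says.** Study Design gives the active arm "eight tele-delivered health coach sessions and three tele-based outcome assessments". It then itemises the sessions, starting with an introductory one: "The following six sessions address behavioral determinants, followed by a final session designed to be a booster session to the overall program".

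Proposed Analyses describes, among participants receiving the intervention, how physical activity, disability and depression change according to the "proportion of the total sessions completed, and 2) the proportion of individual sessions completed". It expects this to "help us estimate optimal dose of the intervention (for example, whether completion of 4 vs. 7 vs. 8 of 10 sessions produces similar outcomes". It adds that the analysis "may inform which specific sessions are absolutely critical". The closing paragraph of that section, on formative evaluation, takes the idea further and aims to "understand how implementation factors influence the optimal dose of our intervention".

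No model, dose categories, similarity margin or confounder adjustment is given for this analysis. Two nearby items bear on it:

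- Enrolment and retention will be broken down by several factors, including "initial cLBP and depression severity using cross-classification tables".
- Distance to a facility is named as a covariate for the exploratory outcome analyses. It is the only covariate named in the section.

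**The concern.** There are two faults in one paragraph. The first is a session total that disagrees with the programme's definition, in an analysis whose exposure is a proportion of that total.

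The second is that the stated purpose goes beyond the design. Participants are randomised to intervention or waitlist, not to a number of sessions. People who complete four sessions may differ at baseline from those who complete eight. The plan's own conceptual model (Overview of Proposed Intervention) "emphasizes motivation to change as a key behavioral determinant", so readiness could plausibly affect both attendance and outcome. The retention table can show imbalance in severity, but it does not adjust the dose contrast and does not cover readiness.

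The Specific Aims say the results will inform methods and procedures for a larger trial. Similar average change at four and eight sessions could reflect baseline differences, or simply a wide interval. It would not by itself show that four sessions are enough.

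**Working it through.** **Session count.** From Study Design: 1 introductory + 6 on behavioral determinants + 1 booster = 8. This matches the stated eight. Adding the three assessments gives 11, so that does not explain the 10 either.

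| Sessions completed | Divisor 8 | Divisor 10 |
|---|---|---|
| 4 | 50% | 40% |
| 7 | 87.5% | 70% |
| 8 | 100% | 80% |

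Dividing by a different constant changes labels, not ranks or tests.

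**Precision.** The one input from the plan is 25 randomised to the intervention (Study Design). The rest are assumptions: all 25 have outcome data, the group splits are as shown, and there is no covariate adjustment. The plan gives no attendance distribution and no precision figure to reproduce. The 95% half-width for a difference between groups of size a and b, in outcome SDs, is t × √(1/a + 1/b).

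- Best two-group split, 12 v 13: 2.069 × √(1/12 + 1/13) = 2.069 × 0.400 = 0.83 SD.
- Three groups of about 8, as the 4, 7 and 8 example suggests, with the SD pooled over 25 (22 df): 2.074 × √(2/8) = 1.04 SD per pair.
- A single session missed by few people, if 20 have data: 5 v 15 gives 2.101 × √(1/5 + 1/15) = 1.08 SD; 3 v 17 gives 2.101 × √(1/3 + 1/17) = 1.32 SD.

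**Linear trend over all 25.** The half-width for 8 v 4 sessions is 4 × 2.069 / (s × √24), where s is the SD of attendance. For assumed s of 1.5, 2.0 and 2.5 sessions this is 1.13, 0.84 and 0.68 *residual* SD. These units are not directly comparable with the outcome SDs above. Baseline adjustment would shrink the residual SD by an amount the documents do not let us compute. In the most favourable case shown, the residual SD would have to fall to about 0.5/0.68 = 0.74 of the outcome SD before the half-width reached 0.5 outcome SD.

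**Similarity.** The plan states no margin, so take 0.5 SD as an assumption. Every group half-width above exceeds 0.5, so even an observed difference of zero would leave the interval outside the margin. Sample sizes per group for 80% power at a true difference of zero:

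- Non-inferiority, one-sided 0.025: 2 × ((1.960 + 0.842)/0.5)² = 62.8, so 63.
- Two one-sided tests at 0.05: 2 × ((1.645 + 1.282)/0.5)² = 68.5, so 69.

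**Confounding, illustration only.** I simulated 25 people with no dose effect and one shared factor acting on both attendance and improvement. With an assumed loading of 0.5 on each, the mean correlation was about 0.23 and p < 0.05 occurred in about 21% of runs. With 0.3, the figures were about 0.08 and 6%. The loadings are invented; the documents give none.

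**The case against.** The strongest defence is that the plan only describes. Its verbs are cautious, the 10 sits inside a parenthetical example, dose is not a named aim, and interviews also feed the dose question. Most of this stands and keeps the point small. It does not remove the stated purpose of estimating an optimal dose, which the comparison cannot serve.

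Several stronger readings are tempting, and the documents do not support them:

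- *Full completers will be recorded as 80%.* Nothing says 10 will be the divisor, and Study Design fixes the total at eight.
- *Similar outcomes could not be shown at all.* That depends on a margin the plan does not state. A margin wide enough could be met with an estimate near zero.
- *About 32 per group would be enough.* That is the size at which the half-width reaches 0.5 SD (1.999 × √(2/32) = 0.4997). It would show similarity within 0.5 SD only if the observed difference were essentially zero.
- *The analysis will be unadjusted.* The plan states no model. Distance might be meant to apply here, but it would address neither severity nor readiness.
- *The dose effect will be inflated.* Neither the direction nor the size of any confounding is established.
- *Sessions will be dropped on these data.* The plan does not say so.

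The population could also exceed 25, because Study Procedures offers the waitlist arm the programme later. No assessments tied to that later course are scheduled. Even 25 v 25 gives 2.011 × √(2/25) = 0.57 SD, and attendance would still not be randomised.

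**Conclusion.** The point holds and is minor. The 10 is certainly inconsistent with the eight-session programme, with consequences for labels only, and only if it is used. The optimal-dose and critical-session claims exceed what non-randomised attendance, with no stated adjustment for severity or readiness, can support in about 25 people. Unadjusted group comparisons have half-widths of 0.83 SD at best and about 1.04 SD for pairs of 8, too wide to show similarity within 0.5 SD. That conclusion rests on the assumed margin, the assumed splits and complete outcome data; missing data would widen the intervals. The analysis is worth keeping as a source of hypotheses. The feasibility estimates and the randomised comparison do not depend on it.

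**What to change.** 1. In Proposed Analyses, change 10 to 8 and state that the denominator is 8.
2. Report change in RMDQ, PHQ-9 and physical activity by number of sessions attended, as a trend with 95% confidence intervals. Adjust RMDQ and PHQ-9 each for its own baseline score, and physical activity for the baseline level that Study Design assigns to session one. Because the pedometer is mailed between sessions one and two, name the measure that supplies that baseline. Describe baseline readiness (PSOCQ, contemplation ladder) by attendance as a summary only; with 25 people, finer cross-tables would be very sparse.
3. Replace the optimal-dose and critical-session wording with, for example: *Associations between attendance and outcome, overall and by individual session, are hypothesis-generating; they do not by themselves establish a sufficient dose or identify critical sessions.* Apply the same limit to the formative-evaluation paragraph where it relies on attendance, but not to its interview evidence.

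The cost is one digit, one sentence, one covariate per model and a short summary. Table 2 already collects RMDQ, PHQ-9, PSOCQ and the contemplation ladder at baseline. The downsides are a weaker dose claim for the larger trial's application and residual confounding that adjustment will not remove.
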